11.8.3 Physical Examinations and Vital Signs (Treatment Cohort)

A PE of all body systems and vital signs assessment will be performed at Day 1 and select study visits. At other visits, symptom-directed PEs and symptom-directed vital sign assessments can be performed at the discretion of the investigator or healthcare provider.

A PE includes a review of the following systems: head/neck/thyroid; eyes/ears/nose/throat (EENT); respiratory; cardiovascular; lymph nodes; abdomen; skin; musculoskeletal; and neurological. Breast, anorectal, and genital examinations will be performed when medically indicated. Any clinically significant abnormal findings in physical examinations will be reported as AEs.

Vital signs include blood pressure (systolic and diastolic), temperature (oral), pulse rate, and respiration rate. These will be assessed following a 5-minute rest in the seated or supine position.

11.8.4 Electrocardiograms (Treatment Cohort)

Standard 12-lead ECGs will be performed using a machine with printout according to the Schedule of Assessments (Table 3-1). Additional standard 12-lead ECGs will be performed at any other time if clinically indicated. A window of ± 15 minutes will be allowed around the nominal times for all postdose ECG assessments.

The performance of all ECGs will adhere to the following guidelines:

- The subject will be instructed to rest in the supine position for at least 5 minutes before having an ECG performed.
- The ECG will be performed before any other procedures that may affect heart rate, such as blood draws.

The ECG traces will be manually read at the study site at the Day 1 and Safety Follow-up Visits. A printout of the ECG traces will be made for safety review by the investigator and maintained with source documentation. Clinically significant ECG abnormalities occurring during the study through the Safety Follow-up Visit will be recorded as AEs.

To ensure safety of the subjects, a qualified individual at the study site will make comparisons to baseline measurements. If the QTcF is increased by >45 msec from the baseline or an absolute QTcF value is ≥ 500 msec for any scheduled ECG, 2 additional ECGs will be performed approximately 2 to 4 minutes apart to confirm the original measurement. If either of the QTcF values from these repeated ECGs remains above the threshold value (>45 msec from baseline or ≥ 500 msec), a single ECG will be repeated at least hourly until QTcF values from 2 successive ECGs fall below the threshold value that triggered the repeat measurement.

If the QTcF value remains above the threshold value (>45 msec from the average of the 3 predose values on Day 1 or ≥ 500 msec) on repeated measurement or is noted on >2 occasions with no identified alternative etiology for the increased QTcF study drug, then discontinuation from study drug treatment may be required after discussion with the medical monitor. Subjects in whom treatment is discontinued for increased QTc should have their QTc monitored closely until it normalizes or returns to baseline.

Further details pertaining to ECGs will be provided to sites in a separate document (ECG Manual).

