9 STATISTICAL ANALYSIS

9.1 General Considerations

Continuous variables will be summarized using the following descriptive summary statistics: the number of subjects (n), mean, standard deviation (SD), median, minimum value (min), and maximum value (max).

Categorical variables will be summarized using counts and percentages.

Visit Windowing Rules: [Section 11.1](#) defines the windows for protocol-defined visits. Note, spirometry assessments, BMI, weight, and height will be used for both efficacy and safety purposes. Their measurements will follow the visit windowing rules for efficacy parameters.

The windows will be applied for both scheduled and unscheduled visits. If no measurement is available within a visit window, the assessment will be considered missing for the visit. If there is more than one measurement available within the same visit window, the following rules will be used:

For all safety parameters, if there are multiple measurements within a visit window, then

- The record closest to the target day will be used, with the exception of the threshold analysis in which the worst record will be used.
- If there are multiple records within the same distance of the target day, the latest record will be used.
- The SFU visit will not be windowed; instead, the nominal visit will be used in relevant analyses.

For all efficacy parameters, if there are multiple measurements within a visit window, the record at the scheduled visit will be used. Otherwise,

- If there are multiple records with the same distance to the target day, the latest record will be used.
- If there are no measurements at the scheduled visit, then the record closest to the target day will be used.

- Assessments at the Early Treatment Termination (ETT) Visit will follow the windowing rules for regular visits.
- Assessments at SFU Visit will follow the windowing rules for regular visits if they fall within the upper boundary of the window for the last scheduled visit. If assessments occur after the upper boundary of the window for the last scheduled visit, they will be still considered as the SFU Visit.

Incomplete/Missing data will not be imputed, unless otherwise specified.

Outliers: No formal statistical analyses will be performed to detect or remedy the presence of statistical outliers, unless otherwise specified.

Unscheduled **Visits:** Unscheduled visit measurements will be included in the following:

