9.7.3 Electrocardiogram

The raw values and change from baseline values will be summarized at each scheduled visit for Safety Set during 110 TE Period: PR, QT, and QTc for HR interval (QTcF), QRS duration, and HR. The number and percentage of subjects with at least 1 threshold analysis event during the entire 110 TE Period will be summarized by treatment group. The threshold analysis criteria are listed in [Section 11.3](#).

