 - Day 1 post-dose and Day 15 pre-/post-dose measurements will be analyzed based on nominal visit names.
 - On Day 1, the pre-dose measurements will be performed in triplicate, the average of the triplicate will be used as pre-dose measurement on Day 1. Only pre-dose measurement with nominal visit names related to the triplicate shall be used in this average.
- The visit window in the above table will still apply for the ECG data after Day 15.

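### After Day 15, the by-visit QTcF summary can replace a scheduled ECG that triggered retesting with a later same-day repeat below the trigger

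*Protocol*

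**What the plan says.** **Retesting (Protocol 11.8.4).** The rule starts as follows: "If the QTcF is increased by >45 msec from the baseline or an absolute QTcF value is ≥ 500 msec for any scheduled ECG". Two more ECGs are then taken 2 to 4 minutes apart. If either is still above the trigger, "a single ECG will be repeated at least hourly until QTcF values from 2 successive ECGs fall below the threshold value".

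**Record selection for safety parameters (SAP 9.1, repeated in SAP 11.1 note 4).** "The windows will be applied for both scheduled and unscheduled visits". The record closest to the target day is chosen, except that the threshold analysis takes the worst record. "If there are multiple records within the same distance of the target day, the latest record will be used".

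**Record selection for efficacy parameters (SAP 9.1).** "For all efficacy parameters, if there are multiple measurements within a visit window, the record at the scheduled visit will be used". Safety parameters have no such preference.

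**ECG special handling (SAP 11.1).** Day 1 post-dose and Day 15 ECGs go by nominal visit name, and the Day 1 predose value is the average of the triplicate. Beyond that, "The visit window in the above table will still apply for the ECG data after Day 15". Safety Follow-up is not windowed for safety parameters.

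**Output (SAP 9.7.3).** "The raw values and change from baseline values will be summarized at each scheduled visit for Safety Set during 110 TE Period". QTcF is among the parameters. SAP 9.1 summarises continuous variables by n, mean, SD, median, minimum and maximum.

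**The concern.** Whether a subject's scheduled ECG is replaced depends on its value. An ECG below the trigger is not repeated under this rule, so it stands. An ECG above it sets off repeats that stop only once they are below it, and the tie rule then prefers the last of them. The selection can only replace high values.

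ECGs are a component of the primary safety endpoint. The by-visit summary is the only QTcF output in SAP 9.7.3 resolved by visit; the threshold counts cover the whole treatment-emergent period. In a 96-week safety study, the by-visit summary is where a reader looks to see when prolongation appears and whether it persists. Its maximum and upper tail are the parts affected. The rule also mixes conditions: scheduled ECGs after Day 15 are taken before dosing, while hourly repeats come later in the day.

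**Working it through.** **1. Which ECGs are exposed.** Protocol Table 3-1 schedules ECGs at Day 1, Day 15, Weeks 8, 16, 24, 48, 72 and 96, Early Treatment Termination (ETT) and Safety Follow-up. SAP 11.1 takes Day 1, Day 15 and Safety Follow-up out of the window rule. That leaves Weeks 8, 16, 24, 48, 72 and 96, plus ETT ECGs mapped to a week.

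**2. What the rules do to one series.** Take an illustrative same-day series at such a visit, in msec: 505 (scheduled), 503 and 498 (confirmatory), 497 and 490 (hourly).
- 505 is at or above 500, so retesting starts.
- 503 is still above the trigger, so hourly ECGs follow.
- 497 and 490 are two successive values below 500, so the series stops.
- All five share one study day, so they are equally distant from the target day and the latest is kept.

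The by-visit summary takes 490. The threshold analysis takes 505. Under the efficacy rule the by-visit value would have been 505.

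If neither confirmatory ECG is above the trigger, the series ends at the second of them, which is also below it.

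**3. Size.** The documents give no QTcF variance, so there is no plan figure to reproduce. The size comes from a simulation resting on assumptions that are not in the documents:
- 400,000 subject-visits per scenario;
- QTcF change = mean effect + between-subject deviation + independent within-subject deviation for each ECG;
- baseline QTcF mean 410, SD 18 msec;
- at most 12 hourly repeats, all on the same day;
- one baseline used for both the trigger and the tabulated change.

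| SD between / within, mean effect (msec) | Visits triggering | Change >45, scheduled record | Change >45, latest record | Median drop when triggered (msec) | Fall in visit mean (msec) |
|---|---|---|---|---|---|
| 10 / 10, 0 | 0.08% | 0.08% | 0.00% | 26.8 | 0.02 |
| 10 / 10, 5 | 0.24% | 0.23% | 0.00% | 22.4 | 0.06 |
| 12 / 12, 0 | 0.38% | 0.37% | 0.00% | 26.4 | 0.10 |
| 14 / 14, 0 | 1.16% | 1.15% | 0.01% | 28.1 | 0.34 |
| 14 / 14, 5 | 2.21% | 2.19% | 0.03% | 26.3 | 0.61 |
| 18 / 10, 0 | 1.44% | 1.43% | 0.17% | 15.8 | 0.23 |

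The fall in the mean is roughly the trigger share times the typical drop; in the last row, 0.0144 × 15.8 = 0.23 msec. Against the 1,044 enrolled subjects in SAP 6.2, the trigger shares amount to about 1 to 23 subjects per visit (0.0221 × 1,044 = 23.1), and fewer where subjects have left.

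**4. Laboratory retests.** Protocol 11.8.6 sets liver retests at 48 to 72 hours or 7 ± 2 days in certain cases. Let the scheduled visit fall d days from target and the retest r days later. The retest is chosen when |d + r| ≤ |d|, that is, when d ≤ −r/2. Assume visits are spread evenly over the ± 5 days that Table 3-1 allows from Week 8 on, so that d has 11 possible values:
- r = 2: 5/11 (45%)
- r = 3: 4/11 (36%)
- r = 5: 3/11 (27%)
- r = 7: 2/11 (18%)
- r = 9: 1/11 (9%)

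Liver retests have no rule that stops them once they are below a limit, so the replacement value can be higher or lower.

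**The case against.** The best defence is that nothing important is lost. The threshold analysis uses the worst record and covers >450 (male), >470 (female), ≥500 and increases of >10, >20, >40 and >60 msec (SAP Table 11-5). SAP 9.1 also brings unscheduled records into on-treatment maxima and into listings where appropriate, and clinically significant ECG abnormalities are recorded as adverse events. The by-visit table is descriptive and the mean hardly moves. This stands, and it limits the weight of the point. It does not justify choosing a record by its value in a table that reports a maximum for each visit.

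The effect is also conditional. The repeats must be in the analysis data, the series must finish the same day, and latest must be read by clock time, which the SAP does not define within a day. An ECG Manual, not available here, may say more.

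A reader might infer more than the documents support:
- **That the tabulated change cannot exceed 45 msec once a series is complete.** The site compares with Day 1 of this study: ">45 msec from the average of the 3 predose values on Day 1". The SAP safety baseline precedes the first active dose, which may lie in the parent study. Where the two differ, a repeat below the site's trigger can still be tabulated above +45.
- **That the kept value is normal.** It need only be below the trigger that was crossed, and may be just below it.
- **That all ECGs are affected.** Day 1 and Day 15, the only visits with scheduled post-dose ECGs, and Safety Follow-up go by nominal visit.
- **That a planned SAP figure is affected.** The mean QTc plot is in Protocol 12.3.5.3 but is not listed in SAP 9.7.3.
- **That by-visit and threshold tables should agree.** One takes a single record per visit and the other the worst over the period, so they can differ under any rule.
- **That liver results are biased downward in the same way.** Step 4 shows that displacement depends on timing and has no fixed direction.

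**Conclusion.** The point holds in a limited form. For windowed ECGs after Day 15, the retest rule and the tie rule together replace a triggering QTcF value with a below-trigger repeat in the by-visit summary, and never the reverse. This follows from the text, given repeats in the analysis data and a series completed the same day.

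The damage is to the upper tail and the visit maximum. In the assumed scenarios, 0.1% to 2.2% of subject-visits trigger. The kept value is a median 16 to 28 msec below the triggering one, and changes above 45 msec fall from 0.1–2.2% of subject-visits to 0–0.2%. That last contrast overstates the loss wherever the SAP baseline differs from the Day 1 reference. The mean falls by 0.02 to 0.61 msec.

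It would be wrong to conclude that QTcF prolongation is hidden from the safety analysis, because the threshold counts are unaffected. The change is still worth making: it removes an outcome-dependent choice from a primary safety output at almost no cost.

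**What to change.** Amend SAP 9.1 and 11.1 note 4:
- For by-visit ECG summaries, use the scheduled-visit record when the window holds one; use unscheduled or repeat records only when it does not.
- Where a window holds both a regular scheduled visit and an ETT record, keep the existing closest-to-target rule between those two.
- Apply the same scheduled-first order to by-visit laboratory summaries for consistency.
- Keep the worst-record rule, including repeats, for threshold analyses.

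In the same edit, define latest within a day by clock time and say which record is used when a nominal time point (Day 15, Safety Follow-up) has repeats.

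The cost is a few lines of SAP text and a change of sort order in programming. No new data are needed, and the protocol's retest procedure is not touched.

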11.8.5 Pulse Oximetry (Treatment Cohort)

Arterial oxygen saturation by pulse oximetry will be measured at visits noted in Table 3-1. This will be assessed following a 5-minute rest (seated or supine) and before study drug dosing. At visits when study drug is taken at the site, pulse oximetry will be collected before the morning dose. This is a noninvasive measure of oxygen delivery to the tissues and has been correlated with clinical status and lung function.

11.8.6 Liver Function Test Parameters (Treatment Cohort)

Liver Function Testing

Liver function testing (ALT, AST, GGT, ALP, direct bilirubin, and total bilirubin) must be performed as noted for serum chemistry, while subjects are receiving study drug treatment and at the Early Treatment Termination Visit and the Safety Follow-up Visit. These blood samples should be processed and shipped immediately per the Laboratory Manual.

Subjects with new treatment-emergent ALT or AST elevations of $>3 \times \text{ULN}$ and clinical symptoms must be followed closely, including repeat confirmatory testing performed by the central laboratory within 48 to 72 hours of the initial finding and subsequent close monitoring of ALT and AST levels, as clinically indicated. In addition, if ALT or AST is $>5 \times \text{ULN}$, repeat follow-up levels must be obtained within 7 ± 2 days.

If a subject cannot return to the site for liver function testing, a local laboratory may be used. Elevations in LFTs at the local laboratory must be reported immediately to the medical monitor, and the subject must have the tests repeated and sent to the central laboratory as soon as possible (ideally within 48 to 72 hours).

Study Drug Interruption

Study drug administration **must be interrupted** immediately (prior to confirmatory testing), and the medical monitor must be notified, if any of the following criteria is met:

- ALT or AST $>8 \times \text{ULN}$
- ALT or AST $>5 \times \text{ULN}$ for more than 2 weeks
- ALT or AST $>3 \times \text{ULN}$, in association with total bilirubin $>2 \times \text{ULN}$ and/or clinical jaundice

A thorough investigation of potential causes should be conducted, and the subject should be followed closely for clinical progression.

If no convincing alternative etiology (e.g., acetaminophen use, viral hepatitis, or alcohol ingestion) for the confirmed elevated transaminases is identified, regardless of whether ALT or AST levels have improved, study drug treatment must be permanently discontinued if repeat testing within 48 to 72 hours confirms the initial elevation. Subjects in whom treatment is discontinued for elevated transaminases should have their transaminases monitored closely until levels normalize or return to baseline.

Resumption of Study Drug

If an alternative, reversible cause of transaminase elevation has been identified, study drug may be resumed once transaminases return to baseline or are $\leq 2 \times$ ULN, whichever is higher. Approval of the medical monitor is required before resumption of study drug. Upon resumption of study drug, transaminases should be assessed weekly for 4 weeks. If a protocol-defined transaminase elevation occurs within 4 weeks of rechallenge with the study drug (with confirmation of the initial elevation by repeat testing within 48 to 72 hours), then the study drug must be permanently discontinued, regardless of the presumed etiology.

11.8.7 Ophthalmologic Examination (Treatment Cohort)

Subjects <18 years of age (age on the date of informed consent/assent in the parent study) will undergo a baseline ophthalmologic examination performed by a licensed ophthalmologist within 28 days before enrollment on Day 1 of Study VX14-661-110, which includes:

- measurement of best corrected distance visual acuity of each eye,
- measurement of lens refracting power following cycloplegia (e.g., autorefractor or ophthalmoscopy streak), and
- pharmacologically dilated examination of the lens with a slit lamp.

The baseline ophthalmologic examination must be completed and the results reviewed before enrollment. This examination may be conducted while the subject is participating in the parent study.

If a cataract or lens opacity is identified and determined to be clinically significant by the ophthalmologist at the baseline examination, the subject will be notified. After discussion with the site principal investigator and in collaboration with the Vertex medical monitor, the subject may elect to participate or not to participate in the study. If the subject elects to participate, more frequent ophthalmologic monitoring should be considered.

Subjects who are enrolled in the Treatment Cohort will have ophthalmologic exams as noted in [Table 3-1](#). If a cataract or lens opacity is identified and determined to be clinically significant by the ophthalmologist after dosing, the subject will be notified. After discussion with the site principal investigator and in collaboration with the Vertex medical monitor, the subject may elect to continue or discontinue the study. If the subject discontinues study drug, they should complete the Early Treatment Termination Visit and Safety Follow-up Visit ([Sections 8.1.1.3](#) and [8.1.1.2](#)). If the subject continues, more frequent ophthalmologic monitoring should be considered.

In addition to the baseline examination, an ophthalmologic examination will be performed by a licensed ophthalmologist at the Early Treatment Termination or Safety Follow-Up Visit for subjects < 18 years of age (age on the date of informed consent/assent in the parent study) who discontinue treatment after receiving at least 1 dose of study drug. This examination may be completed at either the Early Treatment Termination or Safety Follow-Up Visit, but must be completed by the date of the Safety Follow-Up Visit.

In addition, on Day 1 of Study VX14-661-110, the following history will be obtained for all subjects, if it was not documented in the parent study:

- history of steroid use
- history or presence of diabetes

- any prior ophthalmologic or optometric examinations
- history of trauma to the eye
- any family history of glaucoma, congenital cataracts, or cataracts arising later in life
- use of corrective lenses (contact lenses or eyeglasses)
- history of prolonged exposure to sunlight or ultraviolet light and use of sunglasses
- history of exposure to secondhand smoke.

11.8.8 Contraception and Pregnancy (Treatment Cohort)

11.8.8.1 Contraception

Participation in this study requires a commitment from the subject and his/her partner to use at least 1 acceptable method of contraception, which must be used correctly with every act of sexual intercourse. Methods of contraception should be in successful use from at least 14 days before the first dose of study drug (unless otherwise noted) and until 90 days following the last dose of study drug.

For female subjects using oral hormonal contraceptives:

1. The oral hormonal contraceptives should be in successful use from at least 60 days before the first dose of study drug (unless otherwise noted) and until 90 days following the last dose of study drug.
2. Female subjects who change their method of contraception to hormonal contraceptive during Study VX14-661-110 must use a second form of approved contraception for at least 60 days after beginning oral contraceptives.

Contraception for the couple is waived for the following:

- True abstinence for the subject, when this is in line with the preferred and usual lifestyle of the subject. Periodic abstinence (e.g., calendar, ovulation, symptothermal, postovulation methods) and withdrawal are not acceptable methods of contraception.
- If the male is infertile (e.g., bilateral orchiectomy). Infertility may be documented through examination of a semen specimen or by demonstration of the absence of the vas deferens by ultrasound before the first dose of the study drug.
- If the female is of non-childbearing potential, per the following:
 - Documented hysterectomy or a bilateral oophorectomy/salpingo-oophorectomy.
 - Postmenopausal: continuous amenorrhea for at least 12 months and serum FSH levels \geq 40 mIU/mL.
 - Has not achieved menarche (has not had her first menstrual period). If a female achieves menarche during the study, she will need to follow acceptable methods of contraception or abstinence.

For subjects for whom contraception methods are not waived due to at least 1 of the reasons cited above, the following are acceptable contraceptive methods for male subjects and their female (non-study) partners, and for female subjects and their male (non-study) partners:

Table 11-2 Acceptable Methods of Contraception

-
- Male vasectomy 6 months or more previously, with a documented negative post-vasectomy semen analysis for sperm.
 - Male or female condom with or without spermicide (either as a single product if commercially available and/or as allowed according to local regulations; otherwise condom and spermicide as separate products).
 - Female bilateral tubal ligation performed at least 6 months previously.
 - Female diaphragm, cervical cap, or vaginal sponge, each with spermicide (where available).
 - Female continuous use of an intrauterine device (non-hormone releasing or hormone releasing) for at least 90 days before the first dose of study drug
 - Female combined (estrogen and progestogen-containing) or progestogen-only oral hormonal contraception associated with inhibition of ovulation if successfully used for at least 60 days before the first dose of study drug or with a second form of approved contraception for at least 60 days after beginning hormonal contraception.
-

Important notes:

- Local requirements may prohibit the use of some of these acceptable methods listed above. Please contact the medical monitor with any questions.
- If applicable, additional contraception requirements may need to be followed according to local regulations and/or requirements.
- Male and female subjects who are not sexually active at the time of screening must agree to follow the contraceptive requirements of this study if they become sexually active.
- Female condom used with male condom (as a double method of contraception) is not an acceptable method of contraception due to risk of tearing; a different acceptable method of birth control must be used as described in [Table 11-2](#).
- Male subjects must not donate sperm after the first dose of study drug, throughout the study, and for 90 days following the last dose of study drug.
- Female subjects and female partners of male subjects should not plan to become pregnant during the study through 90 days following the last dose of study drug.
- Female subjects should not nurse a child from the start of study drug dosing through 90 days following the last dose of study drug.

Other situations that do not fall within the above specifications may be discussed with the Vertex medical monitor on an individual basis.

